5.2. Exclusion Criteria

Participants are excluded from the study if any of the following criteria apply:

MEDICAL CONDITIONS

 Participant has poorly controlled or unstable COPD, defined as the occurrence of any of the following: 
 Acute worsening of COPD (an exacerbation) that is managed with oral corticosteroids and/or antibiotics within 4 weeks of screening. OR More than two exacerbations in the previous 3 months before screening that required a course of oral corticosteroids and/or antibiotics, or for which the participant was hospitalised. Participant has a past or current medical condition(s) or disease(s) that is/are not well controlled and, which in the judgement of the Investigator, may affect participant safety or affect study endpoints. 
 Note: Participants with adequately treated and well controlled concurrent medical conditions (e.g., hypertension) ARE permitted to be entered into this study. Current or chronic history of liver disease or known hepatic or biliary abnormalities (with the exception of Gilbert's Syndrome, and asymptomatic gallstones). Evidence of concurrent significant pulmonary diseases, other than COPD, including (but not limited to): active tuberculosis, lung cancer, clinically symptomatic bronchiectasis, pulmonary fibrosis, asthma or any other respiratory condition that, in the opinion of the Investigator, may compromise the safety of the participants or affect the interpretation of results.

PRIOR/CONCOMITANT THERAPY

 Participant has had a respiratory tract infection treated with antibiotics within 4 weeks prior to screening. Participant requires regular treatment with oral corticosteroids or has received a course of oral or parenteral corticosteroids within 4 weeks prior to screening. Participant requires long-term oxygen therapy. Participant requires treatment with medications considered as strong inhibitors of CYP3A4 (e.g., macrolide antibiotics) up to 14 days before first dose.

PRIOR/CONCOMITANT CLINICAL STUDY EXPERIENCE

 Participation in this study would result in loss of blood or blood products in excess of 500 mL within a 56-day period. Exposure to more than 4 new chemical entities within 12 months before the first dosing day.

PRIOR/CONCOMITANT CLINICAL STUDY EXPERIENCE

11. Current enrolment or past participation in a clinical trial and has received an investigational product within the following period before the first dosing day in this study: 30 days, 5 half-lives or twice the duration of the biological effect of the investigational product (whichever is longer).

DIAGNOSTIC ASSESSMENTS

12. Positive human immunodeficiency virus (HIV) antibody test.
 
13. Positive pre-study drug (except for as results of opioids prescribed for medical reasons and/or inadvertent consumption of poppy seeds, see Section 6.8) /alcohol screening result.
 
14. Presence of HBsAg/anti-hepatitis B core antibodies (IgM) at screening or within 3 months prior to first dose of study intervention.
 
15. Positive hepatitis C antibody test result at screening or within 3 months prior to first dose of study intervention.
 
16. QTcF > 450 msec at screening visit based on the average of triplicate ECGs.
 
17. A positive laboratory confirmation of COVID-19 infection, or high clinical index of suspicion for COVID-19

OTHER EXCLUSIONS

18. History of regular alcohol consumption within 6 months prior to the study defined in Germany as:
 
 • An average daily intake of pure alcohol of > 24 g per day for males and >12 g per day for females. 
19. Sensitivity to the study intervention or components thereof (including CCI [REDACTED], [REDACTED], or drug or other allergy that, in the opinion of the Investigator or medical monitor, or vulnerable participants (e.g., participants in detention, protected adults under guardianship, trusteeship, or committed to an institution by government or juridical order) contraindicate participation in the study.

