1.3. Schedule of Activities (SoA)

1.3.1. Screen and Follow Up

Procedure	Screening ¹ (up to -30 days before Day 1)	Early Discontinuation/Withdrawal Visit (7 ± 2 days post last dose)	Follow Up Phone Call (7 to 14 days post last dose)
Phone Call			X
Informed Consent	X		
Review Inclusion and Exclusion Criteria	X		
Demography	X		
Medical & Disease History	X		
Full Physical Examination (includes height, weight and BMI)	X		
Brief Physical Examination		X	
Alcohol Urine Test	X	X	
Urine Drug Screen	X	X	
COVID-19 Screening ²	X	X	
AE Review		X	X
SAE Review	X	X	X
Concomitant Medication Review	X	X	X
Inhaler Training	X		
Spirometry (FEV1 & FVC) ³	X	X	
Vital Signs ⁴	X	X	
12-Lead Safety ECG ⁵	X	X	
Safety Laboratory Assessment ⁶	X	X	
Urinalysis	X	X	
Serum FSH and Estradiol ⁷	X		
Urine Pregnancy Test	X	X	
HIV, Hepatitis B and C Screening	X		

Procedure	Screening ¹ (up to -30 days before Day 1)	Early Discontinuation/Withdrawal Visit (7 ± 2 days post last dose)	Follow Up Phone Call (7 to 14 days post last dose)
PK Blood Sample		X	

1. Screening may be performed across multiple visits if necessary.
2. To be performed according to local site policy.
3. Pre- and post-bronchodilator FEV1, predicted FEV1 and FVC are needed at screen only.
4. Includes systolic and diastolic blood pressure, heart rate, respiration rate and tympanic temperature
5. Triplicate ECGs will be obtained at screening and single ECGs at all other occasions.
6. Clinical chemistry, hematology.
7. As needed in women of nonchildbearing potential only

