4. STUDY DESIGN

4.1. Overall Design

This randomized, double-blind, placebo controlled, single and repeat dose study will assess the safety, tolerability and plasma PK of GSK3923868 administered as an inhalation powder blend (GSK3923868 **CCI** for inhalation) using the **CCI** **██████████** inhaler in three cross-over treatments to one cohort of participants with stable COPD. The study design schematic is presented in Section 1.2. Study treatment and post-treatment follow-up Schedule of Activities (SoA) Tables are provided in Section 1.3. Treatment sequence and randomization is shown in Table 1.

Table 1 Study treatment sequence and randomization

Treatment Period	Planned Dose	Cohort 1			
		(n=3)	(n=3)	(n=3)	(n=3)
1 (Single Dose)	500 mcg GSK3923868	A	A	A	P
2 (Single Dose)	1000 mcg GSK3923868	P	A	A	A
3 (14-Day Repeat Dose)	1500 mcg GSK3923868	A	P	A	A

A = Active Treatment; P = Placebo Treatment

The total duration of study participation is shown in Table 2.

Table 2 Study duration by treatment

Screen	Treatment Period 1 (500 mcg single dose) plus washout	Treatment Period 2 (1000 mcg single dose) plus washout	Treatment Period 3 (1500 mcg repeat dose)	Follow-up Period	Total Duration
Up to 30 days before first dose	6 days (2 days inpatient + 4 days outpatient)	6 days (2 days inpatient + 4 days outpatient)	15 days (3 days inpatient + 12 days outpatient)	7- 14 days post-dose	64 - 71 days

Participants who meet the study entry criteria will be randomized to receive GSK3923868 inhalation powder or placebo before study intervention administration on Day 1 of Treatment Period 1.

If a participant withdraws prematurely from the study or discontinues treatment early, additional participants may be recruited to start from 500 mcg single dose treatment sequence at the discretion of the Sponsor in consultation with the Investigator.

Single Dose Treatments

Sufficient participants will be screened and those who meet the study entry criteria will be randomized to receive GSK3923868 or placebo using a **CCI** inhaler in a 3:1 ratio with the intention of a minimum of 8 and a maximum of 12 participants to complete the study.

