6.8. Concomitant Therapy

Any medication or vaccine (including over-the-counter or prescription medicines, recreational drugs, vitamins, and/or herbal supplements) or other specific categories of interest that the participant is receiving at the time of enrolment or receives during the study must be recorded along with:

- reason for use
- dates of administration including start and end dates
- dosage information including dose and frequency

The medical monitor should be contacted if there are any questions regarding concomitant or prior therapy.

Participants must abstain from taking prescription or non-prescription drugs (including recreational drugs, and dietary or herbal supplements) within 7 days (or 14 days if the drug is a potential enzyme inducer) or 5 half-lives (whichever is longer) before the start

of study intervention until completion of the follow-up visit, unless, in the opinion of the investigator and sponsor, the medication will not interfere with the study.

Participants are also permitted to use any medicines (e.g., beta-2 agonists, anticholinergics, methylxanthines, inhaled corticosteroids) to control their COPD. Other concomitant medications may be considered on a case-by-case basis by the investigator in consultation with the medical monitor if required.

Concomitant medication for concurrent well controlled medical conditions (e.g., hypertension, arthritis) may be continued, including opioids such as codeine.

Although GSK3923868 is not expected to be a perpetrator or victim of pharmacokinetic drug-drug interactions, strong CYP3A4 inhibitors (e.g., macrolides) are not permitted.

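### Exclusion criterion 5 and the steroid-course part of criterion 6 stop at screening, up to 30 days before first dose, and only partial or discretionary rules cover the gap

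*Protocol*

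**What the plan says.** Protocol Section 5.2 dates its respiratory and steroid exclusions as follows.

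- Criterion 1, first bullet: "Acute worsening of COPD (an exacerbation) that is managed with oral corticosteroids and/or antibiotics within 4 weeks of screening". The preposition is *of*, so the text does not say whether the 4 weeks run before screening, after it, or both.
- Criterion 1, second bullet: "More than two exacerbations in the previous 3 months before screening that required a course of oral corticosteroids and/or antibiotics", or that led to hospital admission.
- Criterion 5: "Participant has had a respiratory tract infection treated with antibiotics within 4 weeks prior to screening".
- Criterion 6 has two parts. The first, "Participant requires regular treatment with oral corticosteroids", carries no date. The second excludes a participant who "has received a course of oral or parenteral corticosteroids within 4 weeks prior to screening".

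Screening is "up to -30 days before Day 1" in the Schedule of Activities (Protocol Section 1.3.1) and "Up to 30 days before first dose" in Table 2 of Section 4.1. Section 1.3.2 repeats the inclusion and exclusion review on Day -1. Nothing says that the windows are then recounted from Day -1 or from first dose.

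Other criteria in the same list do reach first dose. Criteria 8, 10 and 11 count from first dose or first dosing day, and criteria 14 and 15 from screening or first dose. Section 6.8 asks for abstention from other drugs for at least 7 days before the start of treatment, with exceptions, and adds: "Participants are also permitted to use any medicines (e.g., beta-2 agonists, anticholinergics, methylxanthines, inhaled corticosteroids) to control their COPD".

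**The concern.** The trial is meant to describe tolerability in stable COPD. Protocol Section 2.3.1 relies on enrolling only stable participants as one of its mitigations for bronchospasm, and Section 4.1 calls for caution because this is the first exposure in this population. An exclusion that ends at screening does not describe the participant's condition at first dose when the two may be a month apart.

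A participant who took antibiotics for a chest infection, or a short systemic steroid course, after screening may still be recovering on Day 1. Recovery or relapse could then appear as a respiratory adverse event on treatment, as a laboratory value in a flagged range (SAP Section 6.2.1 has absolute limits for neutrophils, eosinophils and glucose), or as drift in FEV1 from the pre-dose baseline. Under Protocol Section 8.3.1, non-serious events between consent and first dose are recorded as medical history, so the adverse event tables would not show the likely cause.

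**Working it through.** **Is the gap real?** Table 2 of the protocol gives a total duration of 64 to 71 days. Adding its parts: 30 + 6 + 6 + 15 + 7 = 64 and 30 + 6 + 6 + 15 + 14 = 71. Both ends match, so a screening interval of up to 30 days is built into the plan.

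**What do the dated windows cover?** Let *s* be the number of days from screening to first dose. A window of 4 weeks (28 days) before screening covers days *s* + 1 to *s* + 28 before first dose.

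- Of the last 28 pre-dose days, criterion 5 and the steroid-course part of criterion 6 cover max(0, 28 − *s*).
- Gap days outside the 7-day rule in Section 6.8, if it applies and no exception is used: max(0, *s* − 7).
- Gap days outside the 14-day rule of criterion 8 (strong CYP3A4 inhibitors, including macrolides): max(0, *s* − 14).

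| Gap *s* (days) | Last 28 days covered by criteria 5 and 6 | Gap days beyond the 7-day rule | Gap days beyond the 14-day rule |
|---|---|---|---|
| 7 | 21 | 0 | 0 |
| 14 | 14 | 7 | 0 |
| 21 | 7 | 14 | 7 |
| 28 | 0 | 21 | 14 |
| 30 | 0 | 23 | 16 |

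Counting the screening day as inside the window moves an entry by at most one day, and the 30-day row still shows 0 covered. A 28-day window counted from first dose would cover 28 of 28 for every *s*; this is a comparison only.

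**Criterion 1, first bullet.** Read as looking back, it leaves the same gap for exacerbations. Read in both directions, it reaches 28 days past screening and covers almost all of a 30-day gap. The text does not settle which is meant.

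**What else applies before first dose?**

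| Provision | Limit |
|---|---|
| Criteria 2 and 4 | Undated; rest on investigator judgement |
| Criterion 17 | COVID-19 only |
| Criterion 6, regular oral steroids | Undated; does not concern a single course |
| Criterion 8 | Strong CYP3A4 inhibitors only, 14 days |
| Section 6.8 | 7 days (14 for potential enzyme inducers) or 5 half-lives if longer; can be set aside if investigator and sponsor see no interference; COPD medicines permitted |
| Sections 6.5.1.1 and 7.1.4 | Exacerbations only; application before first dose not stated |

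**Weight of one participant.** Table 1 in Protocol Section 4.1 has four sequences of 3, three of them on active in each period: 9 active and 3 placebo. One participant is 1/9 = 11% or 1/3 = 33%.

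**The case against.** The strongest reply is that the plan has several layers. The Day -1 review applies every criterion, not just 5 and 6. Criterion 4 lets the investigator exclude for any respiratory condition that could compromise safety or interpretation, which reaches an unresolved infection, and criterion 2 does similar work for poorly controlled conditions. Day -1 also has a brief physical examination and safety laboratory tests, and FEV1 is measured before dosing on Day 1. An infection severe enough to count as an exacerbation may fall under Section 7.1.4. The Section 6.8 exception requires both investigator and sponsor to judge that the drug will not interfere, so it is not a free pass. And 30 days is a maximum.

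Much of this stands, and it rules out several stronger readings that a reader might infer:

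- *That criteria 1, 5 and 6 together define stable COPD and all look back only from screening.* Only criterion 1 defines unstable COPD, its first bullet fixes no direction, and part of criterion 6 is undated. Criteria 5 and 6 are listed under prior and concomitant therapy.
- *That nothing at Day -1 could stop such a participant.* The provisions just listed could. What is missing is a dated rule that covers the whole gap.
- *That the ban on waivers in Section 5 obliges the site to dose.* It bars approving deviations from entry criteria; Section 7.2 lets the investigator withdraw a participant for safety at any time.
- *That the whole set of safety tables starts from an unstable Day 1 baseline.* In Period 1, laboratory samples are scheduled on Day -1, so that sample is normally the laboratory baseline. The spirometry flag compares the 1-hour value with the same day's pre-dose value, so slow recovery does not enter it. SAP Section 4.2.2.2 places change-from-baseline tables outside the primary endpoint.

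The reply does not close the gap for a completed infection or steroid course that the investigator regards as resolved. Outside the limited drug rules, that case rests on judgement alone, although the same list treats such an event as a firm exclusion when it falls just before screening.

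**Conclusion.** The point holds as an inconsistency of anchors with a real but limited consequence. An antibiotic-treated non-COVID respiratory infection, or a systemic steroid course, that starts and ends between screening and first dose meets neither criterion 5 nor criterion 6. How much is uncovered depends on the gap, and the 30-day row is the worst case. Nothing in the documents says how often such an event would occur; the 11% and 33% give the weight of one affected participant, not a likelihood.

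Within the primary endpoint the exposure is through respiratory adverse events and absolute laboratory flags; outside it, through the FEV1 change-from-baseline summary. No hypothesis is tested, and no sample size figure is affected. The counts assume that screening is a single date. Section 1.3.1 allows several screening visits without saying which one anchors the windows; counting from the last would shorten the gap.

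**What to change.** Reconcile the anchors of criterion 1 (first bullet), criterion 5 and the steroid-course part of criterion 6 with the first-dose anchors used elsewhere in Section 5.2. The existing exclusions should also apply to events between screening and first dose in Period 1, and be checked at the Day -1 review already scheduled. The exact window is for the sponsor to choose. The direction of the first bullet of criterion 1 should be stated.

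Separately, reconcile the sentence in Section 6.8 that permits any COPD medicine with criteria 6 and 8, and with that section's own ban on strong CYP3A4 inhibitors. Which medicines are allowed is the sponsor's decision.

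The change is to wording and adds no scheduled visit or test. The cost is an occasional delayed entry: a participant stopped at Day -1 has not been randomised, so would use the single rescreen in Section 5.4, with a new participant number and repeat screening, and a new consent if more than 30 days have passed since the previous signature (Section 10.1.3).

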5.3. Lifestyle Considerations

5.3.1. Meals and Dietary Restrictions

- Standardized meals will be provided while the participant is confined to the clinical unit. At all mealtimes, food will be served only after the completion of protocol specific procedures.
- Refrain from consumption of red wine, Seville oranges, grapefruit or grapefruit juice, from 7 days before the start of study intervention until after the final dose.

- No water is allowed 1 hour before and after dosing, water is allowed ad libitum at all other times
- Participants should fast for at least 6 hours until 1 hour after each dose.

5.3.2. Caffeine, Alcohol, and Tobacco

- Inpatient
 - a. During PK sampling days, participants will abstain from ingesting caffeine- or xanthine-containing products (e.g., coffee, tea, cola drinks, and chocolate) for 12 hours before the start of dosing until after collection of the final PK sample.
 - b. Use of tobacco products will be allowed, but not between 1 hour before and after drug inhalation (see Section 5.1).
 - c. Alcohol consumption is not permitted in the clinical unit or for at least 12 hours prior to clinical visits.
- Outpatient
 - a. Use of tobacco products will be allowed, but not between 1 hour before and after drug inhalation (see Section 5.1).

5.3.3. Activity

- Participants will abstain from strenuous exercise for 72 hours before each blood collection for clinical laboratory tests. Participants may participate in light recreational activities during the study (e.g., watching television, reading).

5.4. Screen Failures

A screen failure occurs when a participant who consents to participate in the clinical study is not subsequently randomized/entered in the study. A minimal set of screen failure information is required to ensure transparent reporting of screen failure participants to meet the Consolidated Standards of Reporting Trials (CONSORT) publishing requirements and to respond to queries from regulatory authorities. Minimal information includes demography, screen failure details, eligibility criteria, information from any previous trials with the same IP, any protocol deviations and any SAEs.

Individuals who do not meet the criteria for participation in this study (screen failure) may be rescreened once, especially for COVID-19-related screen failures. Participants recovered from COVID-19 infections may be rescreened. Rescreened participants should be assigned a new participant number for every screening/rescreening event. Unused reserve participants that meet eligibility criteria are not considered screen failures.

5.5. Criteria for Temporarily Delaying

Not applicable.

6. STUDY INTERVENTION(S) AND CONCOMITANT THERAPY

Study intervention is defined as any investigational intervention(s), marketed product(s), placebo, or medical device(s) intended to be administered to a study participant according to the study protocol.

6.1. Study Intervention(s) Administered

Table 3 Study Intervention(s) Administered

Study Intervention				
Treatment:	Single Dose Period 1	Single Dose Period 2	Repeat Dose (Period 3)	All Treatment Periods
Intervention name:	GSK3923868 [REDACTED] for inhalation.			Placebo to match GSK3923868 [REDACTED] for inhalation.
Type:	Drug			Placebo
Dose Formulation:	[REDACTED] containing inhalation powder blend. Delivered via [REDACTED] device.			
Unit Dose Strength:	500 mcg	1000 mcg	500 mcg	N/A
Dosage Level(s)¹:	[REDACTED] [REDACTED]	[REDACTED] [REDACTED]	[REDACTED] [REDACTED]	Number [REDACTED] to match active treatment.
Route of Administration:	Inhalation			
Use:	Experimental			Placebo
IMP and NIMP:	IMP			
Sourcing:	Provided centrally by the Sponsor			
Packaging and Labelling:	Study Intervention will be provided in a [REDACTED]. [REDACTED] and one 8 g 20% RH maintaining desiccant sachet. Each [REDACTED] will be labelled as required per country requirement.			
Current Name:	N/A	N/A	NA	N/A

¹[REDACTED].

6.1.1. Medical Devices

- The GSK manufactured medical devices (or devices manufactured for GSK by a third party) provided for use in this study are [REDACTED]
[REDACTED]
- Instructions for medical device use are provided in the SRM.

- All device deficiencies, (including malfunction, use error and inadequate labelling) shall be documented, and reported by the investigator throughout the clinical investigation (see Section 8.3.7 and Section 10.7) and appropriately managed by the sponsor.

6.2. Preparation, Handling, Storage and Accountability

- The investigator or designee must confirm appropriate temperature conditions have been maintained during transit for all study intervention received and any discrepancies are reported and resolved before use of the study intervention.
- Only participants enrolled in the study may receive study intervention and only authorized site staff may supply or administer study intervention. All study interventions must be stored in a secure, environmentally controlled, and monitored (manual or automated) area in accordance with the labeled storage conditions with access limited to the investigator and authorized site staff.
- ~~CCI~~ devices will be supplied in bulk. After use, the devices will be placed in a plastic bag, and the bag will be labelled with the participant number, day of dosing, and date. Devices will be disposed of at site after reconciliation is verified by Study Monitor.
- The investigator, institution, or the head of the medical institution (where applicable) is responsible for study intervention accountability, reconciliation, and record maintenance (i.e., receipt, reconciliation, and final disposition records).
- Further guidance and information for the final disposition of unused study intervention are provided in the Study Reference Manual.
- Under normal conditions of handling and administration, study intervention is not expected to pose significant safety risks to site staff. Take adequate precautions to avoid direct contact with the study intervention. In the case of unintentional occupational exposure notify the monitor, Medical Monitor and/or GSK study contact.
- A MSDS/equivalent document describing occupational hazards and recommended handling precautions either will be provided to the investigator, where this is required by local laws, or is available upon request from GSK.

